2. AMENDMENT HISTORY

Amendment No.	Protocol Version No.	Date issued	Author(s) of changes	Details of Changes made

3. SYNOPSIS

Title	Lung Immune Challenge Study: Controlled Exposure to Inhaled Resiquimod (R848) to Study Mechanisms of Inflammation
Internal Reference No.	A096886
Design	Randomised single ascending dose inhaled exposure to Toll-like receptor (TLR)7/8 agonist R848
Participants	Participants without asthma Participants with asthma
Sample Size	36
Duration	3 years
Aims	
 1. To identify a suitable dose of inhaled R848 that induces innate immune responses in the lungs and blood 2. To identify a suitable dose of inhaled R848 that is clinically tolerable
Outcome Measures	
Primary Outcome
 
 i. Change in CXCL10 in serum or induced sputum 24 hours after single ascending dose inhaled R848 
Secondary Outcomes
 
 i. Change in FEV₁ after 1, 4, 8, 24 and 48 hours of single ascending dose inhaled R848 ii. Change in physiological observations (temperature, pulse rate and blood pressure) after 1, 4, 8, 24 and 48 hours of single ascending dose inhaled R848 iii. Change in peripheral eosinophil and lymphocyte counts after 4, 24 and 48 hours of single ascending dose inhaled R848 iv. Change in serum C-Reactive Protein (CRP) after 4, 24 and 48 hours of single ascending dose inhaled R848
Eligibility	Adult males and females between 18 and 60 years of age meeting inclusion and exclusion criteria.

4. ABBREVIATIONS

AE	Adverse event
AR	Allergic Rhinitis
ARwA	Allergic Rhinitis with Asthma
CUH	Cambridge University Hospitals
CCRC	Cambridge Clinical Research Centre
CRF	Case Report Form
CRP	C-Reactive Protein
CT	Clinical Trials
FEV ₁	Forced Expiratory Volume in First Second
FVC	Forced Vital Capacity
GCP	Good Clinical Practice
HLRI	Heart and Lung Research Institute
ICF	Informed Consent Form
LPS	Lipopolysaccharide
NHS	National Health Service
PBMC	Peripheral Blood Mononuclear Cell
PI	Principal Investigator
PIS	Participant Information Sheet
R&D	NHS Trust R&D Department
R848	Resiquimod
REC	Research Ethics Committee
REDCap	Research Electronic Data Capture
RPH	Royal Papworth Hospital
SAE	Serious Adverse Event
SAR	Serious Adverse Reaction
SOP	Standard Operating Procedure
SUSAR	Suspected Unexpected Serious Adverse Reactions
TMF	Trial Master File

5. BACKGROUND AND RATIONALE

5.1 *Background*

Acute respiratory viral infections cause significant morbidity, especially in vulnerable individuals and has been a topic of immense significance during the recent COVID-19 global pandemic. Respiratory diseases such as asthma and chronic obstructive pulmonary disease (COPD) involve inflammation of the airways and viruses are a major cause of exacerbations (1). Whilst new biological drugs targeting allergic and eosinophilic immune pathways have been developed for chronic allergic asthma, therapeutic options for treating acute asthma attacks remain limited and rely on decades-old blunt tools such as oral corticosteroids.

Development of new therapies and vaccines to combat viral respiratory tract infections is slow, partly because of the limited understanding of immune responses at the respiratory mucosal site of disease (2). Detailed characterization of such responses can facilitate biomarker definition for respiratory diseases, providing mechanistic insights and a platform for the testing of novel therapeutics.

The innate immune system is crucial for effectively detecting and mounting responses to respiratory viruses. Toll-like receptors (TLRs) inside cells play a critical role in the initial detection of viral nucleic acid. TLR7/8 specifically detects RNA viruses such as influenza, rhinovirus, and coronavirus. Airway epithelial and immune cells express TLR7/8 and are therefore vital in mounting appropriate innate immune responses to viral infections (3-5).

Resiquimod (R848) is a synthetic compound that binds to TLR7/8. As R848 activates anti-viral responses, it has been given systemically to treat viral hepatitis C infection (6) and employed topically as a skin cream for actinic keratosis (7). Related TLR7 agonists have been developed for therapeutic use by repeated dose intranasal administration to target allergic inflammation in healthy volunteers and those with allergic rhinitis (8, 9). A TLR7 agonist has also been trialled by the nebulised route and found to activate anti-viral innate immune responses (as evidenced by a rise in the biomarker CXCL10) in the lungs and blood (10). R848 can therefore be used as a suitable translational approach for studying innate immune responses in humans.

5.2 *Rationale*

An intranasal R848 human challenge model has been established by the Principal Investigator (PI). In total, it has been administered intranasally to 54 volunteers at different doses and is well tolerated with no reported serious adverse events (SAE) (11, 12). Nasal R848 induces anti-viral innate immune responses (interferons and chemokines) in a similar manner to respiratory viruses. It therefore represents a very useful research tool for studying innate immune responses to viral infections in the respiratory tract without needing to use live viral challenge, which is significantly more technically and resource intensive.

Intranasal R848 has been given to healthy volunteers and those with allergic rhinitis (AR) or allergic rhinitis with asthma (ARwA). Individuals with AR and ARwA have increased nasal mucosal interferon and chemokine responses compared to healthy volunteers highlighting that dysregulated respiratory mucosal innate immune responses are likely to be important in determining the clinical outcome of viral triggers in individuals with allergy and asthma (12).

The nose however has a different microenvironment, structure and composition of cells compared to the lungs (13). Furthermore, in those with asthma, distinct changes occur in the lungs such as airway remodelling and airway smooth muscle hypertrophy (14). It is therefore crucial to study host innate immune responses directly at the site of disease.

Defining the cellular basis and molecular drivers of innate immune responses to respiratory

viral infections in the lungs will help provide mechanistic insights into how these responses might be dysregulated in diseases and help identify potential therapeutic targets.

The goal of this study is to develop a human lung immune challenge model using controlled exposure to inhaled R848. The aim is to build upon the already established nasal challenge model to identify a clinically tolerable dose for use in the lungs that induces anti-viral innate immune responses. It will first be trialled in healthy individuals and subsequently in volunteers with asthma.

Once established, inhaled R848 challenge is a clinical research approach that will enable:

- Study of the effect of different host states on respiratory innate immune responses
- Understanding of the molecular and immune drivers of asthma exacerbations
- A platform for testing the efficacy of anti-inflammatory compounds
- Significant practical advantages over live viral challenge models

6. OBJECTIVES

6.1 Primary Objectives

- i. To identify an appropriate dose of inhaled R848 which induces innate immune responses in serum and lungs

6.2 Secondary Objectives

- i. To assess clinical tolerability of inhaled R848 with regards to FEV₁
- ii. To assess clinical tolerability of inhaled R848 with regards to physiological observations (temperature, pulse, blood pressure)
- iii. To assess change in peripheral eosinophil and lymphocyte counts after inhaled R848
- iv. To assess change in serum CRP after inhaled R848

7. STUDY DESIGN

7.1 Summary of Trial Design

Nasal administration of R848 has been shown to cause dose-dependent (10 to 100 µg/mL) induction of mucosal innate immune responses (11, 12). The current study will aim to nebulise R848 into the lower airways using a similar dosing regimen and using a nebulisation technique well established using inhaled lipopolysaccharide (LPS) challenge (15). The design of the study is broadly based on a previously published clinical trial of an inhaled TLR7 agonist (10).

Single ascending dose (0.1, 1, 10, 100 µg/mL) nebulisation of R848 will be performed in healthy volunteers (up to n = 24) and subsequently in volunteers with asthma (n = 6).

All volunteers will receive only a single dose and the starting dose cohort for nebulised challenge will be 100-fold lower than the dose administered in the nose to ensure clinical tolerability.

For each dose-cohort (n = 6), participants will be randomised to either R848 (n = 4) or saline (n = 2).

A summary of the study design is outlined in [Appendix A](#).

The study will start with a small “sample only” cohort of six participants without asthma who will be recruited for the collection of nasal brush, sputum, and blood samples to optimise sample processing protocols prior to the main study.

7.2 Primary Outcome Measures

- i. Change in CXCL10 in serum or induced sputum 24 hours after single ascending dose inhaled R848

7.3 Secondary Outcome Measures

- i. Change in FEV₁ after 1, 4, 8, 24 and 48 hours of single ascending dose inhaled R848
- ii. Change in physiological observations (temperature, pulse rate and blood pressure) after 1, 4, 8, 24 and 48 hours of single ascending dose inhaled R848
- iii. Change in peripheral eosinophil and lymphocyte counts after 4, 24 and 48 hours of single ascending dose inhaled R848
- iv. Change in serum CRP after 4, 24 and 48 hours of single ascending dose inhaled R848

8. TRIAL PARTICIPANTS

8.1 Overall Description of Trial Participants

The study will start with a small “sample only” cohort of six participants without asthma who will be recruited for the collection of nasal brush, sputum, and blood samples to optimise sample processing protocols prior to the main study.

The interventional part of the study will be performed in participants without asthma (n = 24), and subsequently in participants with asthma (n = 6).

8.2 Inclusion Criteria

- Male or female aged between 18 and 60 years.
- Willing and able to give informed consent for participation in the study.
- Female participants of child-bearing potential and male participants whose partner is of child-bearing potential must be willing to ensure that they or their partner use effective contraception during the study.
- Clinically acceptable laboratory measurements and ECG at enrolment.
- Ability to expectorate sputum.
- Optional additional swab for SARS-CoV-2 testing will be collected from participants if required by local or/and national health and safety policies at the time of sampling.

For volunteers without asthma:

- No clinical history of asthma
- Normal baseline spirometry i.e. FEV₁/Forced Vital Capacity (FVC) ratio z-score greater than the lower limit of normal.

For volunteers with asthma:

- Physician-diagnosed mild to moderate asthma which is not poorly controlled as evidenced by an Asthma Control Questionnaire (ACQ-5) score of ≤ 1.5 .
- They are permitted to be on inhaled corticosteroids (ICS), long-acting beta agonist (LABA) and long-acting muscarinic antagonists (LAMA).
- Pre-bronchodilator FEV₁ $\geq 70\%$ predicted.
- Evidence of bronchial hyperreactivity as evidenced by either (i) Bronchodilator reversibility (increase FEV₁ $\geq 12\%$ and 200 mL); (ii) Positive methacholine challenge (PC₂₀ $< 8\text{mg/ml}$), or (iii) Positive challenge test as per current CUH policy.

8.3 Exclusion Criteria

- Upper respiratory tract infection in preceding 14 days.
- Lower respiratory tract infection in preceding 28 days.
- Female participants who are pregnant, lactating or planning pregnancy.
- Respiratory diseases (other than asthma where specified).
- Significant extrapulmonary medical conditions.
- Extreme obesity (BMI >40).
- Any other significant disease or disorder which, in the opinion of the Investigator, may either put the participants at risk because of participation in the study, or may influence the result of the study, or the participant's ability to participate in the study.
- Participants who have participated in another research study involving an investigational product in the past 12 weeks.
- No newly prescribed courses of medication including corticosteroids in the four weeks before first study dose other than mild analgesia, vitamins, and supplements.
- Smoking tobacco or vaping products in previous 6 months.

- Smoking history of >5 pack years.

8.4 Treatment Assignment and Stratification

A web-based randomisation and treatment allocation system using REDCap (Research Electronic Data Capture) will be used. Participants will be stratified by sex to ensure equal allocation to active and saline groups.

For each dose cohort of 6 participants, individuals will be randomised (2:1) to either:

- Nebulised R848
- Nebulised Saline

The PI (or delegate) will prepare the solution for nebulisation in a location away from the participant. When it is administered to the participant, they will be unaware of the intervention to which they have been allocated.

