10.2 Dose Escalation

The following doses of nebulised R848 will be tested using a single dose escalation design: 0.1, 1, 10, 100 µg/mL. Six volunteers will be involved in each dose cohort with only a single dose given to each participant.

Each participant will be administered a dose of R848 or saline in a volume of approximately 1 mL (optimal volume to be confirmed after testing) using a breath-actuated nebuliser.

At the end of each dose cohort, CXCL10 levels in sputum and blood will be assessed and compared between saline and R848. If there are no statistically significant differences

between groups, and the dose is tolerable for volunteers, then the study will proceed to the next dose cohort.

Spirometry will be monitored regularly after inhaled challenge. Bronchodilator drugs will be available on standby for administration if volunteers have symptoms of breathlessness or tight chest associated with a significant drop in FEV₁ ($\geq 20\%$) from baseline.

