12. STATISTICS

12.1 *Description of Statistical Methods*

CXCL10 will be measured in sputum and serum 24 hours after each ascending dose of inhaled R848 (n = 4) and compared to inhaled saline (n = 2). CXCL10 levels will be compared between groups using unpaired t-tests.

Spirometry (FEV₁), physiological assessments (temperature, pulse, blood pressure) and leukocyte differential counts from FBC samples measured after challenge will be compared to baseline values using one-way analysis of variance (ANOVA).

12.2 *The Number of Participants*

Nasal R848 is a suitable method of inducing nasal innate immune responses (evidenced by a rise in interferon levels) in healthy individuals and those with asthma (11, 12). Therefore, it is anticipated that inhaled R848 will have a similar effect in inducing lung and peripheral innate immune responses even in a small number of participants.

The number of participants in each dose cohort of the dose finding phase of the study (n = 4 R848, n = 2 saline) is based on AstraZeneca's clinical trial of their inhaled TLR7 agonist (a compound with similar effects) (10), and was a suitable number of participants for assessing innate immune responses as evidenced by a rise in CXCL10 in sputum and serum.

12.3 *The Level of Statistical Significance*

A P-value of < 0.05 will be taken to indicate statistical significance.

12.4 *Procedure for Accounting for Missing, Unused, and Spurious Data.*

Missing clinical data points will be imputed as the mean of values from that volunteer.

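### Does stratifying by sex conflict with the fixed four R848 and two saline participants in each dose cohort?

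*Combined protocol and SAP*

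**What the plan says.** Section 8.4 (Treatment Assignment and Stratification) places randomisation in REDCap and says: "Participants will be stratified by sex to ensure equal allocation to active and saline groups". It then gives the ratio: "For each dose cohort of 6 participants, individuals will be randomised (2:1) to either" nebulised R848 or nebulised saline.

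Section 7.1 gives the counts: "For each dose-cohort (n = 6), participants will be randomised to either R848 (n = 4) or saline (n = 2". Section 12.1 repeats them for the primary comparison, in which CXCL10 is measured "24 hours after each ascending dose of inhaled R848 (n = 4) and compared to inhaled saline (n = 2", and adds: "CXCL10 levels will be compared between groups using unpaired t-tests". Section 12.2 names the same counts as the basis of the cohort size. Section 10.2 uses the comparison to steer escalation: "At the end of each dose cohort, CXCL10 levels in sputum and blood will be assessed and compared between saline and R848".

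Section 8.2 admits both sexes ("Male or female aged between 18 and 60 years") and sets no sex quota. The text available gives no block size. It does not say whether sex strata are nested in cohorts or run across the study. The Appendix A flowchart is not visible in that text.

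**The concern.** Two things look wrong on a first reading.

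The first is the wording. Equal allocation to the two groups sounds like 1:1, while the next statement in section 8.4 is 2:1. Read literally as 1:1 within each sex, it cannot be reconciled with 4:2 for any sex mix.

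The second remains under the sensible reading, that men and women are to be spread evenly over the arms. Six people with two saline places cannot be split in exact proportion by sex unless the number of men is a multiple of three. Recruitment decides that number, and section 8.4 does not say which condition gives way.

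The arm counts matter. Each cohort's CXCL10 comparison rests on six people and feeds the decision to escalate. If separate 2:1 lists per sex were used with no cap per cohort, some cohorts could end with a single saline participant. The t-test would then be weaker, and an unequal-variance version could not be computed.

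**Working it through.** **The plan's own figures.** 4/2 = 2:1, as section 8.4 states. Four dose cohorts of six in participants without asthma, six with asthma and six in the sample-only cohort give 24 + 6 + 6 = 36, the sample size in the synopsis. The counts agree with each other.

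**When exact balance and 4:2 coexist.** Inputs: six people and two saline places (section 7.1); number of men m, not fixed (section 8.2). Exact proportionality needs saline men = m × 2/6 = m/3, a whole number only for m = 0, 3 or 6. With each sex assumed equally likely, P(m = 0, 3 or 6) = (1 + 20 + 1)/64 = 34.4%, so 42/64 = 65.6% of cohorts have another mix. For 30% or 70% men the figure is 69.6%.

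**Two conditions this needs.** Section 8.4 states neither.

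- *Strata nested in each cohort.* If sex is balanced across the four cohorts without asthma, cohorts with 1, 1, 2 and 2 men, of whom 0, 0, 2 and 2 receive R848, are each 4:2. Men total 4:2 and women 12:6. Both conditions are met exactly, although no cohort has 0, 3 or 6 men.
- *Exact rather than approximate balance.* With 4:2 held fixed, near-balance is feasible for any m. Two men split 1:1 and four women split 3:1 give 4:2 in total.

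**Departures from 4:2.** A list constrained to 4:2 gives 0%. For comparison, take the adverse build: separate 2:1 lists per sex, with no cap per cohort. Block size is an assumption because the plan gives none.

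With blocks of three restarted in each cohort, m = 0, 3 or 6 always gives 4:2. For m = 1, 2, 4 or 5, the number of saline participants is 1, 2 or 3 with probability 2/9, 5/9 and 2/9. At equal sex mix, 0.656 × 2/9 = 14.6% of cohorts have one saline participant, 14.6% have three and 70.8% have two.

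Power of the unpaired t-test (4 degrees of freedom, two-sided 0.05, equal variances) for assumed true differences in SD units:

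| Difference | 5:1 | 4:2 | 3:3 | Average, blocks of three | Loss v 4:2 |
|---|---|---|---|---|---|
| 1 SD | 0.110 | 0.147 | 0.159 | 0.143 | 0.004 |
| 2 SD | 0.290 | 0.422 | 0.463 | 0.409 | 0.013 |
| 3 SD | 0.546 | 0.737 | 0.783 | 0.716 | 0.021 |
| 4 SD | 0.778 | 0.924 | 0.948 | 0.906 | 0.018 |

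Average = 0.146 × (5:1) + 0.708 × (4:2) + 0.146 × (3:3).

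**Sensitivity to block size.** Blocks of six per sex give R848:saline splits of 4:2 in 48.3% of cohorts, 5:1 and 3:3 in 23.3% each, and 2:4 and 6:0 in 2.5% each. The 2:4 split has the power of 4:2, and 6:0 allows no test. At 3 SD the average is 0.483 × 0.737 + 0.233 × (0.546 + 0.783) + 0.025 × 0.737 + 0.025 × 0 = 0.684, a loss of about 5 points. The size therefore depends on the assumed list, but every such list breaks the counts in sections 7.1 and 12.1.

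**The case for a change.** The best case for a change is that separate lists are the natural way to implement stratification by sex, and that averages hide the bad cohort. Under blocks of three, the chance that at least one of five cohorts departs from 4:2 is 1 − 0.708^5 = 82%. A cohort with one saline participant has power 29% instead of 42% at 2 SD, and 55% instead of 74% at 3 SD. Each comparison drives its own escalation step, and a clarifying sentence would cost almost nothing.

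The arithmetic stands, and so does the criticism of the wording: equal allocation is a poor phrase beside 2:1, and the nesting of strata is unstated. The step to harm does not stand. It requires someone to build a list that can produce five or three R848 participants when section 7.1 and section 12 state four and two, and section 8.4 itself gives 2:1 for each cohort of six. Nothing in the plan lets sex balance override those counts. The proposed sentence would record a precedence that the documents already imply.

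**Conclusion.** No change is needed. The 0, 3 or 6 rule is correct, but it applies only if sex strata are nested in cohorts and balance must be exact. The plan requires neither. Holding 4:2 fixed and spreading the sexes as evenly as the mix allows satisfies a sensible reading of section 8.4 for every cohort, and it leaves the planned analysis as it is, since the t-test does not include sex.

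Built that way, 0% of cohorts depart from 4:2. The 14.6% with one saline participant, the 14.6% with three and the average power loss of about 2 points at most assume equal sex mix and uncapped blocks of three restarted per cohort. Uncapped blocks of six raise the loss to about 5 points. These figures describe lists that contradict the plan's stated counts. What remains is loose wording and a missing implementation detail, which may also be covered in the flowchart that could not be seen.

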9. STUDY PROCEDURES AND ASSESSMENTS

A schedule of study procedures in relation to study visits is outlined in [Appendix B](#).

9.1 Study Procedures

9.1.1 Nasosorption

Nasal mucosal lining fluid will be collected non-invasively using nasosorption at baseline (0 hours) and 24 hours after intervention to assess whether immune changes in the lungs can also be detected in the nose.

9.1.2 Nasal Brushing

- A small cytology brush will be used to gently and non-invasively collect epithelial cells from the nasal inferior turbinate to enable epithelial cell culture in the laboratory.

9.1.3 Blood

Blood will be collected on the following occasions:

- *Screening (31.5 mL)*: For routine safety and eligibility (9 mL), DNA testing (2.5 mL) and blood for isolation of peripheral blood mononuclear cells (PBMCs) (20 mL).
- *Baseline (14 mL)*: At 0 hours for full blood count (FBC) (4 mL), CRP (5 mL) and serum collection (5 mL).
- *Post intervention (52 mL)*: At 15 minutes, 1 hour, 4 hours, 24 hours and 48 hours for serum collection (25 mL); At 4 hours, 24 hours, and 48 hours for full blood count (FBC) (12 mL) and CRP (15 mL) measurement.

Therefore, a total volume of approximately 100 mL blood will be collected from each volunteer throughout the whole trial including the screening and main study period.

9.1.4 Induced sputum

This will be performed using hypertonic saline at the screening visit and 24 hours after intervention using standardised techniques (16) over a 15-20 minute period to obtain sputum that can be analysed for CXCL10 levels. Salbutamol will be co-administered as a bronchodilator to reduce the chances of bronchoconstriction.

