9.4.1 Visit 1 (Day 1)

This will take place over 24 hours including an overnight stay in the CCRC. Baseline assessments will include:

- Spirometry
- Physiological observations (temperature, pulse, and blood pressure)
- Nasosorption - to determine baseline nasal immune profile
- Blood tests (FBC, CRP, Serum)

Volunteers will have been randomised to receive either R848 or saline via a breath-actuated nebuliser ([Aeroeclipse II](#)). After administration, they will be monitored at regular intervals by the clinical research team to check for clinical tolerability and repeat blood tests. The following morning after 24 hours, volunteers will subsequently have repeat blood tests as well as a repeat induced sputum performed.

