11. SAFETY REPORTING DEFINITIONS

11.1 *Adverse Event (AE)*

An AE or adverse experience is any untoward medical occurrence in a participant, which does not necessarily have a causal relationship with the intervention. An AE can therefore be any unfavourable and unintended sign (including an abnormal laboratory finding), symptom or disease temporally associated with the study, whether or not considered related to the study.

11.2 *Serious Adverse Event (SAE)*

A serious adverse event or reaction is any untoward medical occurrence that at any dose:

- Results in death,
- Is life-threatening,

NOTE: The term "life-threatening" in the definition of "serious" refers to an event in which the participant was at risk of death at the time of the event; it does not refer to an event which hypothetically might have caused death if it were more severe, including an event which:

- Requires inpatient hospitalisation or prolongation of existing hospitalisation,
- Results in persistent or significant disability/incapacity, or
- Is a congenital anomaly/birth defect.
- Other important medical events*

*Other events that may not result in death, are not life threatening, or do not require hospitalisation, may be considered a serious adverse event when, based upon appropriate medical judgement, the event may jeopardise the patient and may require medical or surgical intervention to prevent one of the outcomes listed above.

Planned admission to hospital for a pre-existing condition will not be considered an SAE.

11.3 *Expected Adverse Events and Serious Adverse Events Exempt from Recording*

Nasal R848 challenge administered at doses between 10 - 100 µg/mL in healthy participants and those with asthma has previously been well tolerated with no reported SAEs (11, 12).

R848 is a synthetic substance that when given to in the respiratory tract is designed to mimic the effects of a viral infection such as influenza. Therefore, expected AEs that participants may experience include transient flu-like symptoms such as:

- Cough
- Runny nose
- Mild headache
- Low grade fever
- Lethargy
- Myalgia

If a high-grade fever occurs that is more sustained or causes symptoms, then volunteers will be offered an antipyretic such as paracetamol.

Participants with asthma will be carefully monitored after R848 dosing. If their FEV1 drops by >20% then they will be administered nebulised salbutamol as a bronchodilator.

Nasal sampling using nasosorption and nasal cytology brush may cause:

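### Section 12.1 has no rule for FEV₁ and temperature readings taken after a bronchodilator or antipyretic, so the reported tolerability changes are biased towards baseline

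*Combined protocol and SAP*

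**What the plan says.** Section 7.3 lists as secondary outcomes "Change in FEV₁ after 1, 4, 8, 24 and 48 hours of single ascending dose inhaled R848" and "Change in physiological observations (temperature, pulse rate and blood pressure) after 1, 4, 8, 24 and 48 hours". Section 6.2 ties both to clinical tolerability.

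Three medicines can affect these readings:

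- **Rescue bronchodilator.** Under section 10.2 it is on standby "if volunteers have symptoms of breathlessness or tight chest associated with a significant drop in FEV₁" of at least 20% from baseline. Section 11.3 has salbutamol given to participants with asthma when FEV₁ drops by more than 20%, with no symptom condition.
- **Antipyretic.** Under section 11.3, if a high-grade fever is more sustained or causes symptoms, "volunteers will be offered an antipyretic such as paracetamol".
- **Salbutamol with sputum induction.** Section 9.1.4 says of induction: "This will be performed using hypertonic saline at the screening visit and 24 hours after intervention". It adds: "Salbutamol will be co-administered as a bronchodilator to reduce the chances of bronchoconstriction".

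On the order of events at 24 h, section 9.4.1 says only: "The following morning after 24 hours, volunteers will subsequently have repeat blood tests as well as a repeat induced sputum performed". Spirometry is not mentioned there, and Appendix B gives no order within the 24 h visit.

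For the analysis, section 12.1 says that FEV₁, temperature and the other observations "measured after challenge will be compared to baseline values using one-way analysis of variance (ANOVA". Section 12 has no rule for readings taken after any of these medicines, and rescue use is not an outcome. Section 12.4 fills missing clinical points with the mean of that volunteer's own values.

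**The concern.** Rescue is triggered by the quantity being measured. A participant with a large FEV₁ fall may receive a bronchodilator, and one with a high fever may receive an antipyretic. Later readings then show the reaction plus its treatment, but section 12.1 takes them as the change after R848. The shift is towards baseline and is largest in the participants who react most. Comparison with the 0 h reading does not remove it, because that reading precedes any bronchodilator given by the study that day.

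The reading that triggered rescue may also lie outside the analysed outcome. Appendix B schedules spirometry and observations at 15 minutes, but the outcome times in section 7.3 start at 1 h. Section 10.2 also has spirometry monitored regularly, so a fall could be found at an unscheduled check.

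At stake is how well the trial reports the tolerability of each dose, which is the second aim in the synopsis. With four R848 recipients per dose, one reactor matters to the mean.

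**Working it through.** **The plan's own figures.** The plan gives no power, SD, effect size or rescue rate for FEV₁ or temperature, so there is no figure of that kind to reproduce. The sample size does reproduce: 4 doses × 6 = 24, plus 6 with asthma, plus 6 sample-only = 36. Each dose cohort has 4 on R848 and 2 on saline (section 7.1).

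**One reactor among four.** Assumed: a 25% fall at 1 h that would have lasted to 8 h, rescue after the 1 h reading, 5% below baseline at 4 and 8 h, and no change in the other three. Mean fall = (sum of the four falls) / 4.

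| Time | Without rescue | As analysed |
|---|---|---|
| 1 h | 25/4 = 6.25% | 25/4 = 6.25% |
| 4 h | 25/4 = 6.25% | 5/4 = 1.25% |
| 8 h | 25/4 = 6.25% | 5/4 = 1.25% |

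The fall stays visible at 1 h, and 6.25 − 1.25 = 5 points of mean fall are lost at 4 and 8 h. If the same fall were found and treated at 15 minutes, and the participant read 5% below baseline from 1 h on, the outcome times at 1, 4 and 8 h would all show 1.25%. The 6.25% would be on file but outside the section 7.3 outcome.

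**Range over the assumed response to rescue** (25% fall, others unchanged):

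| Reading after rescue | 1 of 4 reacts (6.25% untreated) | 2 of 4 react (12.5% untreated) |
|---|---|---|
| 15% below | 3.75% | 7.5% |
| 10% below | 2.5% | 5% |
| 5% below | 1.25% | 2.5% |
| 0% | 0% | 0% |

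**Simulation of a strongly reacting dose.** All inputs are assumptions: n = 4, baseline plus five times, 20,000 runs, α = 0.05; mean changes of −15, −22, −20, −12 and −4% at 1, 4, 8, 24 and 48 h; between-person SD of the change 8 points at the −22% level; within-person SD 4 points; between-person CV of FEV₁ from 0 to 15%. Rescue at a drop of 20% or more recovers 50% or 75% of the drop and carries over to the next same-day reading.

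- *Triggering reading kept.* A drop of at least 20% stays visible in 99% of runs. The 8 h mean moves from −20% to −12.8% (50% recovery) or −9.3% (75%). One-way ANOVA power at a CV of 15% falls from 31% to 18% or 13%; at a CV of 0 it falls only from about 94% to 93% or 89%.
- *Triggering reading replaced by one taken after rescue.* The 4 h mean moves from −22% to −13.7% or −9.5%, and a drop of at least 20% is visible in about 10% or 0% of runs.
- *Induction salbutamol alone, assumed to add 5 points.* Only the 24 h mean moves, from −12% to −7%. Power is not reduced (31% against 33%).

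Temperature was not quantified, because the documents give no figures for it. The reasoning is the same.

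**The case against.** The strongest reply is that the worst readings are not lost. An FEV₁ trigger means that the fall is measured before the bronchodilator is given. A reader might infer that the planned analysis replaces the worst reactions with treated values, but no passage says the triggering reading is overwritten. In the example the 1 h mean shows the fall in full. This stands. What remains is that later readings are still shifted, and that a triggering reading at 15 minutes or at an unscheduled check is not among the outcome times.

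A reader might also infer that a poorly tolerated dose would pass as tolerable and the trial would escalate. The documents do not support this. Section 10.2 requires the dose to be tolerable but does not define the word or link it to the ANOVA. Section 11.5 records all adverse events with severity and action taken, so a treated reaction should be on the case report form.

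Three further limits apply:

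- Induction salbutamol can reach only the 24 h reading, and only if spirometry follows induction. The wording of section 9.4.1 is compatible with induction coming last.
- It is tempting to say that salbutamol would cancel a 12% fall in asthma, because section 8.2 accepts reversibility of at least 12% and 200 mL. Only those who qualify by that route are covered. Their number is unknown and could be zero.
- The baseline cannot be called unmedicated, because section 8.2 permits long-acting bronchodilators in asthma and no withholding is stated.

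Finally, analysing all observed values regardless of rescue is a legitimate choice. It has to be stated, however, with rescue use reported beside it, and the plan does neither.

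**Conclusion.** The concern holds for the reported secondary tolerability outcomes. As written, section 12.1 uses medicated FEV₁ and temperature readings as if they were unmedicated, which biases the reported changes towards baseline, most in those who react most. Own-mean imputation under section 12.4 can carry the same values into gaps.

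Under the assumed example, one reactor in four hides 5 points of mean fall at 4 and 8 h while the 1 h mean is unaffected. Over the assumed post-rescue readings of 15% to 0% below baseline, 2.5 to 6.25 points are hidden. The size depends on the rescue rate and on the degree and duration of recovery, none of which the documents give. The exposure of the 24 h reading to induction salbutamol is a separate and narrower gap, conditional on an order that is not stated. An effect on escalation is possible but not shown.

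**What to change.** 1. State that the 24 h FEV₁ used in the analysis is taken before the salbutamol given for sputum induction.
2. Record the time of each bronchodilator and antipyretic dose, and keep the reading that triggered it.
3. Add to section 12.1, as the main tolerability summary, each participant's largest FEV₁ fall before any bronchodilator and highest temperature before any antipyretic, including the 15-minute reading, by arm and dose. Keep the section 7.3 time-point values as observed, with post-medication readings flagged, as a supporting analysis.
4. Report rescue bronchodilator and antipyretic use by arm and dose.

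The cost is wording in section 12.1, one line on the order of measurements at 24 h, and time fields on the case report form. No visits are added, because the readings are already scheduled or already needed to trigger rescue. A worst-value summary shows less of the time course; the supporting analysis retains it.

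No change to rescue treatment is proposed. Sections 10.2 and 11.3 word the bronchodilator trigger differently (at least 20% with symptoms, against more than 20% in asthma with no symptom condition) and must be reconciled.
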